#### **1.6 Multiplicity**

Although there is only one efficacy study endpoint and one safety study endpoint, the assessment of primary and secondary endpoints as well as the repeated measurement of the primary efficacy endpoint over time warrants the implementation of a conservative alpha allocation strategy. Common methods for handling endpoint multiplicity as suggested by Bonferroni and Tukey are useful adjustments for establishing significance levels and hypothesis testing (Hochberg et al). Moreover, a hierarchical test procedure (i.e., fixed sequence procedure) will be followed in order to reflect the relative clinical importance of the null hypothesis for the primary and secondary endpoints. The fixed sequence procedure tests hierarchically ordered hypothesis in sequence until at a 0.05 significance level until first non-rejection. Once a hypothesis is not rejected, no further testing will be performed. It is assumed that

the overall study hypothesis is more important than the primary and secondary endpoint hypotheses and the primary endpoint hypotheses are more important than the secondary endpoint hypotheses.

All analysis will be performed using SAS Analytics Pro, Version 9.3 and JMP Statistical Software, Version 13.2 (SAS Institute Inc., Cary, NC or MedCalc Statistics for Biomedical Research, Version 18.1, MedCalc Software, Belgium, EU.

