This study design involves outcome variables measured on binomial, ordinal, and continuous scales. For the continuously scaled outcome variables (i.e., 10MWT, 6MWT, WISC-II Score, etc.), the general situation applies analysis of variance and covariance when there are  $g$  distinct groups with a sample of observations for each group. The general null hypothesis is that the outcome variable distribution is the same for the treatment and the active control group. The assumptions associated with the analysis of variance are: 1) the  $g$  samples are independent random samples, 2) the observations in group  $i$  (for each  $i = 1, 2, \dots, g$ ) are a random sample from a normal probability distribution with mean  $\mu_i$  and variance  $\sigma_i^2$ , and 3) the  $g$  population variances,  $\sigma_1^2, \dots, \sigma_g^2$ , are equal to a common variance  $\sigma^2$ . Inherent to these assumptions is the assumption of a linear additive model with equal sample sizes. There are a variety of statistical procedures for the comparison of means in an analysis of variance setting. In the case of unequal sample sizes and multiple endpoints, the Scheffe's or Bonferroni procedures are appropriate to control for experiment-wise multi-comparison error (Woolson, 1983). If the assumption of normal distributions is not met, rank analysis of variance is used. More common rank analysis of variance tests are Kruskal-Wallis and Friedman tests. In addition, paired t-Test will be used for paired data since this is a single group matched-pairs design with the assumption that the pairwise differences are normally distributed.

Multiple comparison analysis (repeated measures) of ordinal or nominal-scale data (i.e., 5-point Likert type scales, numeric rating scales, etc.) generally assumes a logit model. This type of model uses cumulative logits, which automatically take the ordinality of the data into account. If the assumptions associated with this model are met, tests of uniform association and proportional odds can be computed. If, however, maximum likelihood estimation is desirable, generalized logits are computed from a log-linear model (Agresti, 1990 and Stokes et al., 1995).

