The one-sided alpha levels are fixed at 0.05 for each of the two one-sided tests and desire a power of 80% when the two gait speeds are the same true mean gait speed.

*Safety:* The occurrence of adverse events, if any, will be recorded, thoroughly investigated, documented and included in the study safety analysis. A determination will be made regarding the relationship of the adverse event to the intervention.

*Null Hypothesis:* The difference in the proportion of active control group subjects who experience a device-related adverse event and the proportion of subjects in the Ekso G intervention group to have experienced a device-related adverse event will be zero.

$$H_0: p = p_0 \text{ vs } H_a: p \neq p_0$$

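### SAP 1.6 stops the fixed sequence at the first non-rejection and does not exempt the zero-difference safety null, so an equally safe Ekso would close all secondary testing

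*SAP*

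**What the plan says.** SAP 1.3 (Primary Endpoint) has an efficacy part and a safety part. The safety null concerns the difference between the active-control proportion and "the proportion of subjects in the Ekso G intervention group to have experienced a device-related adverse event will be zero"; the zero refers to the difference, not to the Ekso proportion. The displayed form is "H_0: p = p_0 \text{ vs } H_a: p \neq p_0": a two-sided alternative, no margin, and no value for p0.

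SAP 1.6 (Multiplicity) begins "Although there is only one efficacy study endpoint and one safety study endpoint", so it counts safety beside efficacy. It then says that "a hierarchical test procedure (i.e., fixed sequence procedure) will be followed", with each step tested at 0.05, and that "Once a hypothesis is not rejected, no further testing will be performed". The overall study hypothesis ranks first, then the primary endpoint hypotheses (plural), then the secondary ones. The section does not number the tests, exempt safety or call it descriptive.

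Two other places bear on this. SAP 1.4 requires a responder to be free of intervention-related complications, and SAP 1.5 builds the overall hypothesis on responders. SAP 1.1, on binomial variables, mentions two-sample chi-square tests of equivalence but gives no margin.

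**The concern.** A fixed sequence suits hypotheses whose rejection is the desired result. Here the desired safety result is that Ekso and standard gait training do not differ, and under a zero-difference null that is a non-rejection. If the safety hypothesis is one of the primary hypotheses in the sequence, an equally safe device ends testing before any secondary endpoint (6MWT, TUG, Berg Balance Scale, quality of life, therapist workload). The analyst would then have to give up confirmatory secondary testing or depart from the SAP after seeing the data. Non-rejection with about 38 per arm would not show equal safety either, so the step buys nothing in return.

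**Working it through.** **Inputs.** From SAP 1.8: 38 Ekso, 38 active control and 19 passive control; mean changes (SD) of 0.11 (0.18), 0.078 (0.108) and 0 (0.108) m/s. From SAP 1.3: the 0.055 m/s margin. From SAP 1.5: the 0.15 margin. The documents give no adverse event rates, so every rate below is an assumption.

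**The plan's own two-proportion figure.** SAP 1.8 states 82% power for 0.85 against 0.55 with 38 per arm, two-sided 0.05. With average proportion 0.70:

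- numerator: 0.30 − 1.96 × √(2 × 0.70 × 0.30 / 38) = 0.30 − 0.206 = 0.094
- denominator: √((0.85 × 0.15 + 0.55 × 0.45) / 38) = 0.0993
- power: Φ(0.094 / 0.0993) = 82.8%, which reproduces the plan.

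No power is stated for the safety test.

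**The safety step alone.** For x events on Ekso and y on active control, with pooled proportion p̄ = (x + y)/76, the chi-square test rejects when |x/38 − y/38| / √(p̄(1 − p̄) × 2/38) exceeds 1.96. With 2 events on active control, 8 on Ekso are needed: p̄ = 10/76 and z = 0.158/0.0775 = 2.04. Summing the two binomial distributions over all rejecting outcomes gives:

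| True rates, Ekso / active | Chi-square rejects | Fisher rejects |
|---|---|---|
| 5% / 5% | 4.1% | 0.3% |
| 10% / 10% | 5.8% | 1.5% |
| 20% / 20% | 5.0% | 2.7% |
| 30% / 10% | 61% | 50% |
| 10% / 30% | 61% | 50% |

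An equally safe Ekso therefore fails the step in at least 94% of trials. Full enrolment does not help: 127 × 2/5 is about 51 per arm, where chi-square rejects in 4.4%, 4.9% and 5.0% at equal rates of 5%, 10% and 20%.

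**The whole sequence.** 200,000 trials per scenario were simulated. Working assumptions:

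- A responder gains at least 0.055 m/s and has no complication; the complication rate equals the assumed event rate.
- The overall hypothesis is an unpaired non-inferiority test at 0.15, one-sided 0.05.
- Hypothesis 1 is a two-sided 0.05 test and Hypothesis 2 a one-sided 0.05 non-inferiority test.
- Safety is tested by chi-square after efficacy.

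| True rates, Ekso / active | Overall passes | Overall and efficacy pass | Secondaries reached |
|---|---|---|---|
| 5% / 5% | 48% | 43% | 1.7% |
| 10% / 10% | 48% | 42% | 2.3% |
| 15% / 5% | 28% | 26% | 4.9% |
| 25% / 5% | 13% | 12% | 6.0% |
| 30% / 10% | 13% | 12% | 3.5% |

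At equal rates, of the trials that pass every earlier step only 1.70/43.07 = 3.9% (5% rates) or 2.34/41.96 = 5.6% (10% rates) pass safety. Applying both sides of the equivalence test in Hypothesis 2 would lower the efficacy pass rate; it would not change the safety test.

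**The case against.** **Safety may not be in the sequence.** SAP 1.3 numbers only Hypotheses 1 and 2, both on gait speed, and Protocol 17.2 counts two hypotheses, neither on safety. This stands in part: the place of safety is an inference. It is a fair one, because SAP 1.6 names a safety endpoint beside the efficacy endpoint, ranks the primary hypotheses as a group and exempts none. If safety was meant to stand outside, the SAP lacks the sentence that says so.

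**Equivalence tests are planned.** Under the equivalence tests in SAP 1.1, similar safety would be a rejection. Without a margin they cannot be run, and SAP 1.3 states a difference null.

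**A reader might infer that a more harmful Ekso opens the secondary endpoints.** The 61% for 30% against 10% suggests it. That figure is the safety step in isolation. The overall hypothesis comes first and counts complications against a responder, so only about 3.5% of such trials reach the secondaries, against 2.3% at equal 10% rates. The test is also symmetric: a safer Ekso (10% against 30%) reaches them in about 42%. What stands is narrower: a significant difference in either direction is the only way past the step.

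**A reader might see the same defect in SAP 1.1**, where "The general null hypothesis is that the outcome variable distribution is the same for the treatment and the active control group". That is generic analysis-of-variance text. An equality null is ordinary for secondary difference tests, and for therapist burden, where the protocol predicts an Ekso advantage, rejection is the desired result.

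**The rule is conservative.** It inflates no error rate, and if safety follows gait speed the main conclusions are untouched. This stands and limits the severity.

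**Conclusion.** The rule is wrong as written and should be fixed. On the natural reading of SAP 1.3 with 1.6, equal safety closes secondary testing in about 94% to 96% of trials that reach the safety step (chi-square, equal rates of 5% to 20%), and in more under Fisher's test. Over the whole sequence at equal rates of 5% or 10%, a chance of about 42% of reaching the secondaries falls to about 2%.

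This rests on assumed event rates, on the inferred place of safety, and, for the whole-sequence figures, on the simulation assumptions above. If safety came before efficacy, an equally safe Ekso would close the gait-speed tests as well. The documents do not support the claim that harm generally opens secondary testing.

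**What to change.** State in SAP 1.6 that the safety hypothesis is outside the fixed sequence. Report the Ekso minus active-control difference in the proportion with a device-related adverse event, with a 95% confidence interval and no gating role.

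Then list the remaining order explicitly: the overall study hypothesis, Hypotheses 1 and 2 as the SAP ranks and defines them, and a named list of secondary endpoints with the groups compared for each. Therapist outcomes should be compared between Groups 1 and 2, because Group 3 has no training sessions during the 12-week comparison.

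The cost is SAP wording, settled before outcome data are seen by arm, and the loss of a p-value-based safety claim, which a non-rejection at this sample size could not support. A one-sided safety non-inferiority test would be an alternative, but it needs a justified margin and expected event rates. The documents give neither, so its sample size cannot be derived from them.

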### **1.7 Lost to Follow-up**

Data on subjects who are lost to follow-up or who withdraw from the study will be maintained and analyzed up to the point at which they discontinued. The reason for withdrawal will be recorded if known. Subjects who discontinue participation, for whatever reason, will remain in the study and be subject to follow-up in the same manner as those who complete the study except as noted above. The only confirmed lost to follow-up subject will be the subject who dies or refuses to continue to participate in the study and thereby withdraws.

### **1.8 Sample Size Estimate**

Computations for sample size and power are based on effect sizes derived from internal study data and the relevant clinical literature for the primary endpoint. For the Ekso G intervention group, the postulated effect (derived from internal study data) is a mean change from baseline in gait speed of 0.11 m/s, with a corresponding standard deviation of 0.18 m/s. For the active control group, the postulated effect is a mean change from baseline in gait speed of 0.078 m/s (derived from the relevant clinical literature), with a corresponding standard deviation of 0.108 m/s.

The passive control group is postulated to have a mean change of zero with the same standard deviation as active control, or 0.108 m/s. Sample size and power are then computed for both statistical tests cited above: superiority of Ekso G to passive control and non-inferiority of Ekso G to active control.

Under 2:2:1 randomization with a desired power of 80%, the required sample size for superiority of Ekso G intervention to passive control is 38 subjects with evaluable data in the Ekso G intervention group and 19 in passive control (incorporating the 2:1 Ekso G: passive control randomization). For non-inferiority of Ekso G to active control, the groups are of equal size and the required sample size is 37 per group.

Taking the greater of these numbers for each randomized group, total sample size under 2:2:1 randomization is therefore 38 for Ekso G intervention, 38 for active control and 19 for passive control, a total of 95. To account for possible attrition as well as potential variance from the postulated effects, up to 127 subjects in the randomized group will be enrolled.

With the sample size fixed at 38 in both the Ekso G intervention Group and the Active Control Intervention Group, the power estimate for the detection of a significant difference in the **Overall Study Success Rate** is as follows

- The statistical hypotheses are

$H_0$  (Null hypothesis):  $P_E = 0.850$

$H_a$  (alternative hypothesis):  $P_A = 0.550$

- A two group chi-square test with a 0.05 two-sided significance level will have 82% power to detect the difference between a Ekso G Intervention group proportion,  $P_E$ , of 0.850 and the Active Control Group intervention proportion,  $p_A$ , of 0.550 (odds ratio of 0.216) when the sample size in each group is 38.

When testing the **Overall Study Hypothesis of Equivalence**, a paired test with a 0.025 one-sided significance level will have 80% power to reject the null hypothesis that the proportions are not equivalent (the difference in proportions,  $P_E - P_A$ , is -0.150 or farther from zero in the same direction) when the expected difference in proportions is 0.00, assuming that the proportion of discordant pairs is 0.160 and the sample size is 56 in each intervention group.

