#### **1.5 Overall Study Hypothesis**

The study hypothesis is directly related to the success criteria.

Accordingly, the null hypothesis of the study posits that there is no difference between the success probabilities for the Ekso G intervention and the active control intervention. Therefore, this trial of equivalence compares case success probabilities where the investigational intervention will be considered acceptable only if it can be demonstrated with 95% confidence ( $\alpha = 0.05$ ) that it is, at worst, 15% inferior to the active control intervention ( $\delta = 0.15$ ).

$$H_0: \pi_{\text{Ekso}} - \pi_{\text{Active Control}} \leq -0.15 \text{ vs. } H_a: \pi_{\text{Ekso}} - \pi_{\text{Active Control}} > -0.15$$

where  $\pi_i$  = the probability of subjects who achieve the success criteria that the difference in success probabilities is no more than 15% using the Blackwelder approach to testing equivalence of paired proportions.

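### The responder test that opens the SAP's fixed sequence is a paired test on unpaired arms, sized at 56 per group where the design provides 38 to about 51, and it can block both gait-speed hypotheses.

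*SAP*

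**What the plan says.** - **Test.** SAP 1.5 tests whether the Ekso success probability is more than 0.15 below that of active control, "using the Blackwelder approach to testing equivalence of paired proportions".
- **Power.** SAP 1.8 states that "a paired test with a 0.025 one-sided significance level will have 80% power to reject the null hypothesis", with an expected difference of 0.00 and "assuming that the proportion of discordant pairs is 0.160 and the sample size is 56 in each intervention group".
- **Alpha.** SAP 1.5 says that "the investigational intervention will be considered acceptable only if it can be demonstrated with 95% confidence", without giving sidedness. SAP 1.6 describes a procedure that "tests hierarchically ordered hypothesis in sequence until at a 0.05 significance level until first non-rejection", also without sidedness. Protocol 17.1 uses one-sided 0.05 for non-inferiority.
- **Order.** SAP 1.6 commits to a fixed sequence and takes it that "the overall study hypothesis is more important than the primary and secondary endpoint hypotheses". It adds: "Once a hypothesis is not rejected, no further testing will be performed".
- **Design and size.** Protocol 8.2 randomises individuals by computer to three arms at 2:2:1. On sizing, SAP 1.8 says: "Sample size and power are then computed for both statistical tests cited above: superiority of Ekso G to passive control"; the second of the two is non-inferiority of Ekso to active control. The result is 38, 38 and 19 evaluable (95 in total), with enrolment of up to 127.

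**The concern.** A paired test needs each Ekso participant to be linked to a particular active-control participant. Neither document describes any matching, so the test cannot be carried out as written and a discordant-pair proportion has no meaning here. The SAP also treats the comparison as unpaired elsewhere. In 1.8 the same success rate is powered with a two-group chi-square test, and 1.1 plans two-sample equivalence tests for binomial outcomes.

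The group size behind the 80% is not reconciled with the 38 per arm and the cap of 127 given in the same section.

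The position of this test in the sequence makes the defect serious. If the responder test is not rejected, neither gait-speed hypothesis is formally tested, however strong the gait-speed data are. The 80% power planned for those hypotheses takes no account of a preceding gate.

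**Working it through.** **Inputs.** Margin 0.15, discordant proportion 0.160, true difference 0, one-sided alpha 0.025, power 80%, 56 per group, 38 evaluable per active arm, cap of 127 (SAP 1.5 and 1.8); allocation 2:2:1 (Protocol 8.2).

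**1. The SAP's own figure.** n = f(z₁₋α + z₁₋β)² / δ² = 0.16 × (1.960 + 0.8416)² / 0.15² = 55.8, rounded up to 56. It reproduces. At one-sided 0.05 the same formula gives 43.96, or 44.

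**2. Feasibility.** 56 per active arm needs 56 × 5/2 = 140 randomised. The cap gives 127 × 2/5 = 50.8, about 51 per active arm before attrition.

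**3. The SAP's formula at the sizes available.** Power = Φ(0.15/√(0.16/n) − z₁₋α).

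| One-sided alpha | n = 38 | n = 51 | n = 56 |
|---|---|---|---|
| 0.025 | 64% | 76% | 80% |
| 0.05 | 75% | 85% | 88% |

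These figures show the internal conflict only, since the formula does not apply to unpaired arms.

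**4. What 0.16 implies without pairs.** For independent arms with a common rate p, the corresponding quantity is 2p(1−p). It equals 0.16 only at p = 0.912 (or 0.088). At p = 0.85 it is 0.255, and the simple normal formula then needs 89 per arm at one-sided 0.025 (about 223 randomised) or 71 at one-sided 0.05.

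**5. Exact power for independent arms.** Farrington-Manning score test, margin 0.15, restricted maximum likelihood variance, full binomial enumeration, equal true rates. The SAP gives no common rate for this test, so the rates are assumptions.

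| n per arm | One-sided alpha | 0.55 | 0.85 | 0.90 | 0.95 |
|---|---|---|---|---|---|
| 38 | 0.025 | 28% | 43% | 50% | 64% |
| 38 | 0.05 | 37% | 57% | 67% | 83% |
| 51 | 0.025 | 33% | 53% | 64% | 82% |
| 51 | 0.05 | 46% | 67% | 77% | 92% |
| 56 | 0.025 | 39% | 58% | 69% | 87% |
| 56 | 0.05 | 47% | 71% | 81% | 94% |

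The enumerated maximum size is slightly above nominal (0.028 to 0.030 at 0.025; 0.052 to 0.054 at 0.05), so these powers are, if anything, slightly favourable. An exact calculation for the Wald test at 0.85 and one-sided 0.025 gives 45% at 38 and 59% at 51, so the conclusion does not hinge on the choice of test.

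**6. Chance of blocking gait speed (1 − power) at a common rate of 0.85.** 57% (38 per arm, 0.025), 43% (38, 0.05), 47% (51, 0.025), 33% (51, 0.05). Across rates of 0.55 to 0.95 at 38 or 51 per arm, the range is 8% (0.95, 51, 0.05) to 72% (0.55, 38, 0.025).

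**7. What lies behind the gate.** With the SAP's inputs at 38/38/19, normal approximation:
- Superiority to passive control: SE = √(0.18²/38 + 0.108²/19) = 0.0383; power = Φ(0.11/0.0383 − 1.96) = 82%.
- Non-inferiority to active control at one-sided 0.05: SE = √((0.18² + 0.108²)/38) = 0.0341; power = Φ((0.055 + 0.032)/0.0341 − 1.645) = 82%.

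**The case against.** - **Other rates in the SAP.** For its chi-square statement, SAP 1.8 assumes 0.850 for Ekso and 0.550 for active control. If those were the true rates, the Farrington-Manning test at 38 per arm would have over 99% power at either alpha and would block gait speed in under 1% of trials. That is correct, and the SAP holds two incompatible scenarios. But its power statement for this test assumes a difference of 0.00, so equal rates are its own planning case.
- **The 0.85 rate.** This is the success threshold in SAP 1.4, not a forecast of a common rate. That is fair, and it is why the full range is given.
- **Whether 56 is out of reach.** That depends on alpha: at one-sided 0.05 the paired formula needs 44, which the cap could hold. This stands, but the SAP's figure rests on 0.025, and the pairing would be invalid at either level.
- **A possible unpaired reading.** The simple independent-arm formula also returns 56 at a common rate of about 91%. This does not rescue the statement. No such rate is stated, the exact score test there gives 73% at one-sided 0.025, and the conflict with 38 and 127 remains.
- **How firm the gate is.** SAP 1.6 ranks hypotheses by importance without listing a sequence, and it calls Bonferroni and Tukey adjustments useful. Protocol 17.2 has no responder hypothesis. Even so, the fixed sequence is the procedure to which SAP 1.6 commits, and the stopping rule is explicit.

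**Conclusion.** The concern holds. Three parts need no assumption about responder rates: the paired test does not fit the randomised arms; 56 per group conflicts with the 38 evaluable per arm and the cap of 127; and SAP 1.6 places this test ahead of the hypotheses that determined the sample size. The alpha for the test is also unsettled between one-sided 0.025 and 0.05.

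The size of the harm does rest on assumptions, namely independent arms, equal true rates and a Farrington-Manning analysis. On those terms the first test in the sequence has well under 80% power in most of the scenarios examined at 38 or 51 per arm. It exceeds 80% only at a common rate of 0.95, and not at 38 per arm with one-sided 0.025. A large true advantage for Ekso would remove most of the blocking risk, but SAP 1.8 does not plan this test on one. This must be fixed before any unblinded analysis, because choosing the test, order or alpha afterwards would undermine the confirmatory claim.

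**What to change.** 1. **SAP 1.6.** Remove the responder test as gate and write out one explicit order. First, Hypothesis #1 of SAP 1.3 (Ekso superior to passive control). Second, Hypothesis #2 in the non-inferiority form of Protocol 17.2, margin 0.055 m/s, which is the form SAP 1.8 sizes. Both use the fast 10MWT speed, to which SAP 1.3 gives precedence. The responder hypothesis follows. Protocol 17.2 sets no testing order, so the SAP must. Other orders are defensible, provided the responder test does not precede the gait-speed tests.
2. **SAP 1.5 and 1.8.** Replace the paired method with an independent-groups non-inferiority test of the difference in proportions, margin 0.15, for example Farrington-Manning. Delete the discordant-pair and 56-per-group text.
3. **Alpha.** State a single one-sided level for this test in SAP 1.5, 1.6 and 1.8, and reconcile it with Protocol 17.1.
4. **Power.** Restate it at 38 per arm as a range over explicitly assumed responder rates, computed for the chosen test, and reconcile the 0.00 difference with the 0.850 versus 0.550 scenario. The responder definition, population and time point (SAP 1.4) must be clear before this can be done.

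The cost is SAP wording only, with no added patients or data. The stated power for the responder comparison will look less favourable, and it will no longer be the lead claim.
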